- 1) acceptability of the mindfulness-based intervention and mindfulness practice,
- 2) the changes they experience and their utilisation of mindfulness skills, and
- 3) the broader impact of the mindfulness-based intervention on their family relationships and their lives more widely.

After the last follow-up (12-month post-randomisation) of the pilot trial, a subsample of 20 to 24 young people in the MAC intervention arm (or until data saturation has been reached), will be invited to a qualitative interview. Recruitment will be purposive, including patients across all sites, and seeking to achieve maximum variation in relation to:

- 1) completion/non-completion of treatment,
- 2) response/non-response to treatment (defined as reaching a score below the clinical threshold for depression on the RCADS (Ebesutani et al., 2012)), and
- 3) recruitment site (to examine contextual factors).

Carers of these young people will be invited for separate interviews.

Practice data and written feedback from the intervention app will be used to inform subsampling and will also provide us with the opportunity to explore any unanticipated experiences and effects in more depth. In collaboration with the PPIE members of our team, we will develop, and pilot test, a semi-structured topic guide (**Appendix mi and mii**).

Interviews will be video recorded, transcribed verbatim, and anonymised. Thematic analysis of interview transcripts will be conducted using a Framework approach (Richie et al., 2014), involving the coding and sorting of textual units according to both deductive and inductively derived categories, and the use of matrices to review the coded data, investigate commonalities and differences and search for patterns. Coding and data management will be facilitated by NVivo software.

Exploration of subjective experiences of decentring and mindfulness relating to negative mental events

To better understand the ways in which young people and their carers utilise decentring and mindfulness skills, we will complement questionnaire assessments by asking a subgroup of young people and their carers

to participate in micro-phenomenological interviews, in which they will be asked to describe their subjective experience of dealing with negative mental events (see qualitative analyses below).

The micro-phenomenological approach (Petitmengin et al., 2019) is based on the observation that mental activities are often not immediately accessible to reflective consciousness and uses specific prompts and questions to help participants become aware of the unrecognised or "pre-reflective" part of their experience. The interviews will focus on a singular experience of relating to a negative mental event. Participants will be guided to identify such an event and "evoke" the experience of responding to it while reporting on increasingly finer details in an iterative process.

Interviews will be recorded and transcribed, questions and answers numbered, general statements eliminated, and the remaining content chronologically reorganised to reconstitute the temporal course of the experience. We will follow recommendations for micro-phenomenological analysis by Petitmengin, Remilliey, and Valenzuela-Moguillansky (Petitmengin et al., 2019) first to identify minimal units of meaning and secondly, to abstract from these units to derive generic structures of experience. This will allow us to compare structures between young people and carers as well as between subgroups (completion/non-completion, responders/non-responders) within these two groups (**Appendix mi and mii**).

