Procedures: An individual orientation session serves to brief each adolescent-carer dyad on the aims and structure of the treatment. The themes (learning intentions) of each session are explicit, and the skills are taught sequentially over the course. Skills-teaching in the small group setting is highly experiential, with sessions comprising short exercises, formal and informal mindfulness practices, as well as group discussion. In addition to groups for young people, MAC includes parallel groups for carers or parents. Carer groups follow the same sequential pattern of skills teaching as the adolescent groups, are similarly experiential, and over the same period.

WHO PROVIDED

Depending on therapists' previous experience, MAC groups will be facilitated by either one or two therapists who will receive regular supervision during the delivery of the treatment, further details below. MAC therapists will require competency in both mindfulness and working with young people and their carers, and therefore we will invite therapists who meet the following minimum criteria:

- i) have a core professional training meaning they can work therapeutically with depressed children and young people,
- ii) have experience of running group-based interventions for young people or carers,
- iii) have their own personal mindfulness practice following attendance at either an 8-week MBCT or MBSR group,
- iv) desirably, have experience leading or co-leading a Mindfulness Based Intervention (MBI), ideally with level 1 MBI teacher training.

Therapists will all need to attend specific MAC training which will involve a 5-day training workshop that will include built-in practice and feedback sessions. We will provide weekly online supervision to group leaders. Supervision is especially crucial when practitioners first deliver after training in a new approach.

Detailed data about applicants' previous experience of work with children and young people and their willingness to engage in mindfulness will be gathered to judge suitability of the candidates for the training.

HOW

The intervention will be held in-person in groups, with one site per cohort being remote via videoconferencing.

WHERE

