In-person groups will be held in central locations to maximise attendance, with both young people and parent/carer groups at the same location. Where possible these two groups will run simultaneously to aid travel for the young person and their parent/carer, however, where this is not possible, they will occur in the same week. In person groups will only involve participants from the same site joining together.

Remote groups will be conducted using NHS approved software, for example MS Teams or Zoom. Participants will be encouraged to have their video cameras on during the MAC sessions since we know this improves engagement and this will be emphasised during the orientation meeting. Remote groups will involve participants from multiple sites and will run once enough participants have selected this as an option. All materials that would usually be given in person to participants will be posted to participants' homes or emailed, depending on preference. Remote and in person MAC groups will cover exactly the same content in exactly the same order, their only difference being their mode of delivery.

WHEN and HOW MUCH

The interventions will consist of 8 weekly group-based sessions of 1 hour 30 to 45 minutes duration and a pre-class interview of 1 hour duration conducted with each dyad of a young person and their parent/carer and allowing for individual therapist contact with both. Participants of both groups will be asked to engage

in regular daily home practice consisting of guided meditation and generalisation exercises aimed at helping participants utilise mindfulness skills in daily life.

HOW WELL

- Therapist completed supervision forms indicate issues that therapists wanted guidance about.
- Session checklists will be used to record if all elements of a session were delivered as intended.
- Data from the practice Apps will indicate the number and duration of practice sessions conducted by YP and parents/carers.

Supervision

Therapists will take part in 9 supervision sessions: Week 0 before orientation and session 1 begins, through to week 9 after the final session has been delivered. Therapists will access remote group supervision with experienced MAC therapists. The 60-minute supervision would comprise 45 minutes on the young person intervention and 15 minutes on carer intervention, with a strong focus on overlap. A brief pre-supervision form will be developed, which therapists will complete to highlight demands to discuss at supervision.

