Participants will be asked to record their daily mindfulness practice, either directly via the app or on paper diary cards. We will measure number of times both formal and informal mindfulness has been practiced as well as recording which practices were used. Whilst self-report will be the primary source of this data, we will

cross reference this with metrics recorded directly via the app, for example, the dates, duration, and frequency of log-ons as well as how often each audio recorded mindfulness practice was played.

Health Economic Measures

Cost components included in the health economic analysis will comprise:

- Detailed costs of the MAC intervention,
- Other NHS and social service use during the 12-month within-study period, including:
 - CAMHS, primary care, social care, and community care contacts,
 - \circ prescribed medications,
 - hospital inpatient admissions and outpatient attendances,
 - School attendance and other education-related contacts
- Informal care costs incurred by participants, parents and carers and families, including time taken off work.

The intervention costs will comprise the costs of:

- training the trainers,
- staff time to deliver MAC classes and pre-class orientation interviews,
- non-staff costs associated with delivery of MAC classes (e.g., life or virtual room hire),
- the costs of delivering the app, and
- provision of information materials for participants and families.

The volume of resource use for the non-intervention cost components will be measured in the trial using a bespoke retrospective questionnaire based on a modified version of the Client Service Receipt Inventory, completed by participants for a 12-month period at baseline, 14 weeks, and 12-months post-baseline for each individual participant. These questionnaires will cover the previous 3-month period at baseline and 3 months, and the previous 9-month period at 12 months.

When parents/carers have consented to take part we will ask them to complete this information on behalf of their child. If the young person's parent/carer has not consented for their own involvement, then we will ask the young person themselves to complete this questionnaire.

EQ-5D-5L Quality of Life (Devlin et al., 2018a)

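### The list of MAC intervention costs leaves out therapist supervision and does not say whether the therapists' 5-day training is costed, so as written it understates the cost of MAC

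*Protocol*

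**What the plan says.** **Costing list.** Protocol Section 14, Health Economic Measures, states "The intervention costs will comprise the costs of" and then gives five items:

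- "training the trainers"
- "staff time to deliver MAC classes and pre-class orientation interviews"
- non-staff delivery costs such as room hire
- delivery of the app
- information materials

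**Intervention description.** Section 13, Table 4, says "Therapists will all need to attend specific MAC training which will involve a 5-day training workshop". It also says "We will provide weekly online supervision to group leaders", and under Supervision "Therapists will take part in 9 supervision sessions". Each supervision session lasts 60 minutes and is held remotely, in groups, with experienced MAC therapists.

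**Related commitments.** Section 14 promises detailed MAC costs in general terms. Section 18 promises a detailed cost analysis and a Health Economic Analysis Plan, to be approved before data lock.

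**Resource-use recall.** Section 14 gives the resource-use form at baseline, 14 weeks and 12 months, then says "These questionnaires will cover the previous 3-month period at baseline and 3 months, and the previous 9-month period at 12 months". The outcome tables label the middle visit 3.5 months.

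**The concern.** The cost list is worded as complete. Just above it, the line on other NHS and social service use is introduced as an open list; the MAC line is not. Supervision fits none of the five items, because staff time is confined to classes and orientation interviews. The training item speaks of trainers, whereas Section 13 calls the people who attend the workshop therapists.

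Both activities occur only because MAC is delivered, so a cost left out here comes off one arm alone. The understated incremental cost would enter the within-trial ICER, the net monetary benefit and the acceptability curve. It would also enter the budget-impact analysis in Section 18, where training and supervision are real costs of roll-out.

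The recall wording is a different matter. It concerns non-intervention services, and the question there is whether the two look-back periods cover the year once each.

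**Working it through.** **A. Supervision hours against listed staff hours, per cohort**

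The protocol gives no MAC cost to reproduce, so the comparison is in therapist hours.

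Inputs from Section 13, Table 4:
- 8 sessions of 1.5 to 1.75 h
- parallel young-person and carer groups
- one or two therapists per group
- a 1 h orientation interview per dyad
- 9 supervision sessions of 1 h

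Input from Section 15: group size 12.

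Assumption: one therapist per orientation interview.

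Listed staff hours = 2 groups × 8 × session length × therapists per group + 12 × 1
- One therapist per group: 2 × 8 × 1.5 + 12 = 36 h; 2 × 8 × 1.75 + 12 = 40 h
- Two per group: 24 × 2 + 12 = 60 h; 28 × 2 + 12 = 68 h

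Supervision hours = 9 × number of distinct therapists. That number depends on whether the same people take both groups.

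| Therapists per group | Distinct therapists | Supervision | Share of listed hours |
|---|---|---|---|
| 1 | 1 | 9 h | 9/40 to 9/36 = 22.5% to 25% |
| 1 | 2 | 18 h | 18/40 to 18/36 = 45% to 50% |
| 2 | 2 | 18 h | 18/68 to 18/60 = 26% to 30% |
| 2 | 4 | 36 h | 36/68 to 36/60 = 53% to 60% |

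The overall range is about 22% to 60%. Section 13 prefers the two groups to run simultaneously. That needs separate therapists and points to the second and fourth rows.

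Table 4 also describes supervision as running from week 0 to week 9, which is 10 sessions if weekly. The range is then 10/40 = 25% to 40/60 = 67%. The two statements of the number of sessions need reconciling.

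**B. The workshop, if it is not covered**

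Assumption: 7.5 h per day, so 5 × 7.5 = 37.5 h per therapist. By Sections 10 and 19 a pilot site runs four courses within the trial. Spread over four, the share runs from (37.5/4)/40 = 23% with one therapist to (4 × 37.5/4)/60 = 62.5% with four. Charged to a single course, it runs from 37.5/40 = 94% to 150/60 = 250%. The result depends heavily on the spreading rule.

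**C. Direction**

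ICER = ΔC/ΔE, and incremental net monetary benefit = λΔE − ΔC, where λ is the willingness to pay per QALY. If ΔC is too low by δ > 0, net benefit is too high by δ whatever ΔE is. The ICER moves in MAC's favour when ΔE > 0.

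**D. Recall windows**

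The plan's own total reproduces: 3 + 9 = 12 months. Take a month as 365.25/12 = 30.44 days, so 3 months = 91.3 days, and 14 weeks = 98 days.
- Second form: day 98 − 91.3 = 6.7 to day 98
- 12-month form: day 365.25 − 9 × 30.44 = 91.3 to day 365.25
- Uncovered: days 0 to 6.7
- Counted twice: days 91.3 to 98, again 6.7 days
- Each is 6.7/365.25 = 1.8% of the year

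Error in the cost difference = 6.7 days × (arm difference in daily cost in the doubled week − arm difference in the missed week). With constant use in each arm this is zero.

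**The case against.** The strongest reply is that the list is a summary. Section 14 promises detailed MAC costs, Section 18 defers to a Health Economic Analysis Plan that is not shown, and rules for itemising and annuitising costs usually belong there. That stands for the spreading rule and for how much start-up cost to charge. Section 13 ties the importance of supervision to practitioners' first delivery after training, so part of it may be a start-up cost. It does not remove the inconsistency: the protocol states a definite list that disagrees with its own account of the intervention. Nor does it help that therapist training and the app are set outside this protocol's focus in the Study Summary, because the app is costed all the same.

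A reader might infer that the workshop is certainly left out. The documents do not establish this; the undefined training item may be loose wording for it. What can be asked is that the term be defined.

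A reader might also infer that the recall windows understate MAC cost or favour MAC. They cannot do the first, because Section 14 uses the form only for non-intervention resource use. For the second, the windows are the same in both arms, the gap equals the overlap, and the sign of any residual error is not fixed. Therapy contacts also have a second source: the Treatment Recording Sheet is completed monthly in both arms over the 12 months. Taking the 3.5-month label literally would make the gap and overlap 15.2 days each, but the text repeatedly says 14 weeks (3.2 months), and the label reads as rounding.

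Finally, the percentages are shares of listed staff hours. They are not shares of total MAC cost, nor of incremental cost, which nets off other service use. Section 13 expects less of that use in the MAC arm.

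**Conclusion.** The costing point holds. Applied as written, the list omits therapist and supervisor time in supervision and leaves therapist training unresolved, so MAC cost and incremental cost are too low. Supervision alone is about 22% to 60% of listed staff hours per 12-dyad cohort, before supervisor time, assuming 9 sessions and one therapist per orientation interview. Supervisor time is shared, because supervision is in groups, but it is not zero.

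Net monetary benefit then looks too favourable to MAC; the ICER does so only if the incremental effect is positive. Neither shift can be put in pounds, because the protocol gives no unit costs, therapist numbers, spreading rule or expected QALY difference.

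The recall mismatch is real but minor: about one week missed and one week doubled, for non-intervention use in both arms, with unknown sign. It is a separate point and adds nothing to the case that MAC cost is understated.

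**What to change.** 1. In Section 14, add therapist time in supervision and supervisor time to the list of intervention costs.
2. State that therapist time at the 5-day training is costed, or define the existing training item so that it includes it. Spread it over the courses delivered under a rule set in the Health Economic Analysis Plan.
3. Record these hours. The protocol describes supervision forms on issues needing guidance and session checklists, but no log of training or supervision time.
4. Reconcile the stated number of supervision sessions with the week 0 to week 9 span.
5. Reword the resource-use form to ask about use since randomisation at 14 weeks, and since the 14-week questionnaire at 12 months. This has to be done before participants answer; an analysis plan cannot repair the recall period afterwards.

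The cost is a wording change, a little extra recording, and a stated MAC cost that is less favourable than under the present list.

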11. PARTICIPANT SELECTION

MAC is a second-line clinical intervention, so recruitment and delivery will be from the most appropriate service for each local area:

- CAMHS,
- Mental Health Support Teams (MHSTs), including:
 - o Educational Mental Health Practitioners (EMHPs),
 - Children's Wellbeing Practitioners,
 - o Counsellors or nurses based in schools/school-based mental health teams,
 - Other community wellbeing teams.

Subject inclusion and exclusion criteria

 Table 2: Inclusion and exclusion criteria with justification

Young Person Inclusion Criteria	Identifier	Justification
Aged 15 to 18 years old at the time of	Research	We have increased the minimum age from 14
recruitment.	team.	in the PDG. The mean age in our feasibility
		work was 16.4 years, and 14-year-olds were
		more likely to struggle to engage than their
		older peers (Racey et al., 2018). Similarly, the

		recently completed MY Resilience In ADolescence (MYRIAD) study suggests that older teenagers may be more likely to derive benefit (Montero-Marin et al., 2022). The upper age limit relates to the most common age boundary between most CAMHS and
Completed at least one evidence-based	Referring	adult mental health services.
treatment for anxiety or depression.	clinician.	only be offered after one psychosocial treatment for depression or anxiety has been delivered.
Primary presenting problem of unresolved or relapsed low mood, depression or anxiety who are currently experiencing some symptoms of low mood as evidenced by a score of 20 or above on the 33 item MFQ (COSTELLO & ANGOLD, 1988; Daviss et al., 2006)	Research team.	Comorbidity with any of the problems in the Exclusion Criteria below would not necessarily exclude a young person provided their score at recruitment on the 33 item MFQ (COSTELLO & ANGOLD, 1988; Daviss et al., 2006) is 20 or above
Readiness to engage in a group-based mindfulness-based intervention. This includes the ability to focus and participate in a group for up to 1 hour 45 minutes; capacity to think flexibly and reflect on one's own experiences; and the willingness to practice everyday mindfulness and learn formal meditation for up to 15 minutes per day.	Referring clinician.	This is a requirement to be able to engage in the treatment.

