Carer Inclusion Criteria: A carer of a young person who has consented to take part in the study.	Research team.	Young people will be included regardless of whether one or both carers wish to attend the parallel carer groups. Likewise, parents/carers would be able to continue to attend should the young person withdraw from the study.

Young Person Exclusion Criteria	Identifier	Justification
Current active management required for	Referring	Would struggle to engage with, and derive
suicidal risk, self-harm or eating disorder.	clinician.	benefit from, a group-based MAC intervention
Current psychosis.		from experience of feasibility and PDG.
Current PTSD.	CRIES-8	
	administered	
	by Research	
	team.	
A score of <20 on the MFQ33	MFQ33	MAC is designed to treat depression and low
	administered	mood, therefore are using a cutoff score of 20
	by Research	or above, as it is often used to indicate
	team	clinically significant depressive symptoms.
Carer Exclusion Criteria: A carer of a	Research	The parent group is primarily about
young person who has not consented to	team.	supporting the young people's mindfulness
take part in the study.		practice.

Patient withdrawal/discontinuation from MAC

While we will encourage the young people and parent(s) to attend in tandem, it would be unethical to refuse a willing young person access to the study if their parent was unable or unwilling to attend with them. Likewise, while a parent or carer would only be recruited if their child was initially willing to attend because the parent group is primarily about supporting the young people's mindfulness practice, we would still encourage them to continue should their child withdraw from the trial. Outcome measures will still be taken regardless of any withdrawal from MAC, unless the young person/carer formally withdraws from the trial. More details in the later section COMPLIANCE AND WITHDRAWAL.

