The RCAD-SF (Ebesutani et al., 2012) is a 25-item questionnaire that measures anxiety (15 items) and depression (10 items). Items are scored on a 4-point Likert scale (Never, Sometimes, Often or Always) with higher scores indicating greater levels of psychopathology. Both the depression and anxiety sub-scales show good internal and external validity with good reliability in both a clinical and school-based sample (Ebesutani et al., 2012). The RCADS will be used as a Baseline Moderator (T0) to measure depression severity for stratification, and also be used at T1 and T2 as a secondary outcome measure for anxiety. It will not be used to analyse depression outcomes in young people, as that is measured using the SMFQ as the primary outcome.

Moods and Feelings Questionnaire 33 MFQ 33; (COSTELLO & ANGOLD, 1988; Daviss et al., 2006) The MFQ is a 33-item self-report scale designed to assess depressive symptoms in children and adolescents aged 8 to 18 years. It covers various domains of depression, including mood, anhedonia, and cognitive symptoms. Respondents rate each item based on how they have been feeling or acting recently, with choices ranging from 0 to 2. The total score ranges from 0 to 66, with higher scores indicating greater levels of depressive symptoms. A cutoff score of 20 or above is often used to indicate clinically significant depressive symptoms (Cooper & Goodyer, 1993). The MFQ has demonstrated good internal consistency (α = .89 to .95) and test-retest reliability (r = .79 to .91). Additionally, it has been shown to have good convergent and discriminant validity when compared with other measures of depression (COSTELLO & ANGOLD, 1988; Daviss et al., 2006).

Generalized Anxiety Disorder 7 GAD 7; (Spitzer et al., n.d.-a)

The GAD-7 (Spitzer et al., n.d.-a) is 7-item scale measuring symptoms of anxiety and worry. Items are rated on a 4-point Likert scale (0-3; maximum score 21), with higher scores reflecting greater symptom severity. Scores \geq 10 indicate clinical levels of anxiety. The scale is reported to have excellent internal consistency (α = .89) and good convergent validity (S. U. Johnson et al., 2019; Löwe et al., 2008). Sensitivity and specificity are between 89-74% and 82-54%, respectively when a cut off of 10 is used (Beard & Björgvinsson, 2014).

Ability to 'cope'

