15. STATISTICAL CONSIDERATIONS

Randomisation

 Table 6: Randomisation Summary

Randomised design	Individual patient		
Type of randomisation	Randomly permuted varying length blocks, stratified by:		
to be used			
Stratification variables	- Site		
	- Young person currently taking a therapeutic does of antidepressant: Yes/No		
	- Young person's total RCADS score above a T score of 70 versus a score 70 or		
	below		
Ratio allocation	1:1 ratio		
between treatment			
arms			
How randomisation will	A web-based randomisation system designed and maintained by the King's		
be implemented and	College London Clinical Trials Unit (KCTU) for the duration of the project. Access		
approach to conceal	will be restricted via usernames and passwords to appropriate research team		
allocation	members, and the system will be hosted on a dedicated server within KCL.		
Define the	As this is not a drug trial, and it is not possible to blind the participants and		
circumstances under	certain trial team members to allocation, we will not need a special procedure		
which randomisation	for code breaking. We do not anticipate serious adverse reactions, but if there		
codes may be broken	is a serious adverse event and there is a need for a blinded member of the trial		
and the procedure for	team to know if an individual is in the MAC group, the individual, their carer, or		
doing it	one of the trial therapists can provide this information.		

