Following written consent, participants will be randomised in a 1:1 ratio to one of the two treatment arms (TAU, or MAC + TAU). A web-based randomisation system will be designed, using the bespoke KCTU randomisation system. The randomisation system will be created in collaboration with the trial analyst/s and the CI and maintained by the King's Clinical Trials Unit for the duration of the project. It will be hosted on a dedicated server within KCL. The system will employ block randomisation with randomly varying block sizes and will be stratified by i) site, ii) if the young person is taking a therapeutic dose of antidepressants or not and iii) if their RCADS (Ebesutani et al., 2012) score at baseline indicates that they have severe depression or not. The details needed for randomisation will be held in a dedicated database. Only the Programme Manager, Trial Manager and Programme Administrators (unblinded) will have access to the randomisation system (or their nominated backup in times of absence; the nominated backup will not be another member of the blinded team but will be a team member whose role on the delegation log specifies this role as contingency Trial Manager).

Sample size calculation

Our power calculation suggests that 480 participants (240 per arm, MAC allocation=20 groups) will allow us to detect an effect size of 0.3 with 90% power, allowing for 20% attrition. The calculation assumed using a two-sided independent samples t-test of the difference between arms, alpha = 0.05, assuming a MAC group size of 12, intraclass cluster correlation of 0.05, i.e. a design effect / inflation of $1 + [12 - 1] \times 0.05 = 1.55$ (Williams et al., 2008), one baseline and two post-randomisation measures with correlation rho = 0.5 = deflation factor of 0.5 (Machin et al., 2009), and 20% attrition (Kennard et al., 2009;(Mental Health Taskforce, 2016). The calculation was done using the Gpower software, with methods from Killip et al used to hand-calculate the cluster effect for MAC group (Killip, 2004).

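### Response in the qualitative sub-study is defined by a follow-up RCADS score alone, so young people already below the threshold at baseline can be classed as responders without any change

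*Protocol*

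**What the plan says.** Protocol Section 14, in the subsection on qualitative analyses of the experience of the intervention, plans interviews with 20 to 24 young people from the MAC arm after the 12-month follow-up of the pilot. Sampling aims for maximum variation on three dimensions: completion, response and site. The second is "response/non-response to treatment (defined as reaching a score below the clinical threshold for depression on the RCADS". The rule gives no baseline requirement, no amount of change and no threshold value. The timing of the interviews points to T2, but the rule itself names no time point.

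The next subsection, on micro-phenomenological interviews, compares structures of experience between "subgroups (completion/non-completion, responders/non-responders) within these two groups", that is, young people and carers. It offers no other definition of response.

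Section 11, Table 2, sets the symptom criterion for entry on another scale: "currently experiencing some symptoms of low mood as evidenced by a score of 20 or above on the 33 item MFQ". The matching exclusion is "A score of <20 on the MFQ33". The qualifying problem is a "Primary presenting problem of unresolved or relapsed low mood, depression or anxiety", so primary anxiety is admitted if the MFQ criterion is met.

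The RCADS is completed by young people at T0, T1 and T2. At baseline it serves as a moderator and a stratification factor (Section 15). For depression outcomes, Section 14 says: "It will not be used to analyse depression outcomes in young people".

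**The concern.** A responder label should mean that something changed. This one depends on where the young person ends and not on where they began, and it is read from a scale that did not decide who entered. Someone below the RCADS depression threshold at both T0 and T2 satisfies the words of the definition.

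The label has two uses. As a sampling dimension, it is meant to secure interviewees who did and did not respond; if it also picks up baseline mildness, the intended variation is diluted. As an analytic contrast in the micro-phenomenological work, it is meant to show how responders and non-responders differ in dealing with negative mental events. A difference there could come from initial severity rather than response to MAC. Research questions 8 and 9 in Section 9 are the ones exposed.

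**Working it through.** The plan gives no figure to reproduce. The check has two parts.

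**1. Can a participant start below the threshold?**

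- Entry requires MFQ33 of 20 or above (Section 11). No RCADS score is required or excluded.
- Table 6 in Section 15 stratifies by "Young person's total RCADS score above a T score of 70 versus a score 70 or" below. The text beneath the table describes the same factor as whether the "score at baseline indicates that they have severe depression or not". Both strata are randomised, so lower RCADS scorers are admitted.
- The cut at a total T score of 70 is not stated to be the clinical threshold for depression. It therefore shows that lower scorers enter, but not how many lie below that threshold.

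Nothing in the eligibility rules ensures a start at or above the threshold, so a participant below it at T0 and T2 can be labelled a responder with no change.

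**2. What would it do to the label? (illustration only)**

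Assumptions, none given by the documents for the RCADS:
- baseline and follow-up scores are bivariate normal with equal SD;
- there is no mean change;
- a share q of participants is below the threshold at baseline, taken as 10% to 40%;
- the correlation ρ is 0.5 or 0.8, the two values that Section 15 mentions for the MFQ.

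With threshold c = Φ⁻¹(q):
- share labelled responder = Φ(c) = q;
- share below at both times = Φ₂(c, c; ρ);
- share of labelled responders already below at T0 = Φ₂(c, c; ρ) / q.

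| q | ρ | Below at both times | Share of labelled responders already below at T0 |
|---|---|---|---|
| 10% | 0.5 | 3.2% | 32% |
| 10% | 0.8 | 5.6% | 56% |
| 20% | 0.5 | 8.7% | 44% |
| 20% | 0.8 | 12.9% | 65% |
| 30% | 0.5 | 15.7% | 52% |
| 30% | 0.8 | 21.1% | 70% |
| 40% | 0.5 | 23.9% | 60% |
| 40% | 0.8 | 30.1% | 75% |

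Example: q = 20%, ρ = 0.5 gives 0.087 / 0.200 = 0.44.

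If 24 interviewees resembled the whole arm, between 24 × 0.032 = 0.8 and 24 × 0.301 = 7.2 of them would be responders who began and ended below the threshold. A purposive sample is not meant to resemble the arm, so this gives scale only.

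Allowing a general improvement of 0.5 SD, the share labelled responder becomes Φ(c + 0.5). At q = 20% that is Φ(−0.342) = 37%, and 36% to 47% of those labelled were already below at T0. Improvement lowers the share but does not remove it.

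**The case against.** The strongest reply is that this is a label for choosing interviewees, not an outcome. No effect is estimated from it, completion and site also guide selection, practice data and app feedback inform it, and interviewees are asked what changes they experienced, so an unchanged participant can be recognised in the transcript. This stands as a limit on importance. It does not dispose of the point, because the micro-phenomenological subsection also uses responder status as a comparison.

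The verb in the definition suggests movement from above to below the threshold. That is a fair reading, but it leaves open where a young person already below at T0 belongs: responder, non-responder or neither.

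Three stronger readings are tempting and go too far:

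- *That the definition flatly contradicts the RCADS paragraph.* That paragraph sits among the secondary outcome measures and gives as its reason that depression is measured by the SMFQ. It is about outcome analysis, and selecting interviewees is a different use. The two passages need a clarifying clause.
- *That carers cannot be classified.* Carers do not complete the RCADS, but those invited to the experience interviews are the carers of the sampled young people, so they can take the young person's status. This is simply not written down.
- *That most labelled responders would be spurious.* This depends on q, which the documents do not give. Every entrant scores 20 or above on the MFQ33, a cut-off that the protocol itself says is often used to indicate clinically significant symptoms, so a large q cannot be presumed.

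**Conclusion.** The point holds as a minor one. The written definition has no baseline condition and uses a scale that did not determine entry, so it can mix baseline mildness with response. That follows from the text alone. The size does not: the figures above rest on an assumed share below the threshold, an assumed correlation and normality.

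The effect is confined to the qualitative sub-study. A reader might infer that the trial's depression findings are affected. They are not: the SMFQ area-under-the-curve analysis, the secondary outcomes, the power and the error rates do not use this label.

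**What to change.** In Section 14, define response relative to baseline with data already collected. For example: RCADS depression score at or above a named threshold at T0 and below it at T2. Place young people below the threshold at T0 in a separate category, who may still be interviewed but stand outside the responder contrast. Add two sentences: carers take their young person's responder status; and, in the RCADS paragraph, this use of the depression score is for interview sampling and subgrouping only.

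A baseline-referenced change on the MFQ33 or SMFQ is an alternative. The MFQ33 was used to select entrants, so a rule based on it is exposed to regression to the mean. The five-point MFQ figure in Section 15 is a between-group difference and should not be presented as a validated criterion for individual response.

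The cost is a few sentences and no new data. The drawback is that participants below the threshold at T0 leave the contrast. The repaired rule also still admits chance crossings: at q = 20% with no mean change, (0.200 − 0.087) / 0.80 = 14% of those starting at or above the threshold would cross it at ρ = 0.5, and (0.200 − 0.129) / 0.80 = 9% at ρ = 0.8. The label should therefore be described as a change in status, not as proof of benefit from MAC.
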